Objective 2 is a pragmatic cluster randomized trial. We have partnered with two rural healthcare systems (one in eastern Kentucky and one in Western Kentucky) for this study. Two clinics from each system will be randomized to participate in the intervention (4 total intervention sites) and the remaining clinics will serve as the control sites. The intervention consists of health information technology (including an automated patient identification system and bidirectional e-referral system connecting clinics to the DSMES providers) and a practice facilitation collaborative. The collaborative is a structured, facilitated process that brings together teams from different organizations to learn from one another. The collaborative utilizes the Model for Improvement, a quality improvement approach designed by the Institute for Healthcare Improvement that uses rapid cycle quality improvement – repeated PDSA (plan do study act) cycles meant to identify care quality barriers and rapidly implement and measure change. Teams from intervention clinics will apply this quality improvement strategy to identify and address quality gaps in diabetes care and DSMES utilization at their clinics. Practice facilitators on the study team will provide individualized coaching (practice facilitation) to clinics in the intervention arm of the study. We will assess the effect of the interventions on DSMES referrals (primary outcome), by comparing rates of referrals between intervention and control clinics (clinics within the healthcare system not randomized to the intervention). Secondary outcomes include DSMES attendance, patient satisfaction and diabetes knowledge, A1c control, and intervention feasibility and acceptability.

Objective 3 involves surveys and interviews with clinic staff that participated in the intervention and DSMES providers from the geographic areas where the intervention took place. Interviews will be conducted via phone and audio will be recorded. The goal of Objective 3 is to understand how the various implementation strategies embedded within the practice facilitation collaborative and clinical context influenced DSMES uptake to inform future refinement for program replication and scale-up.

Attachments

Subject Recruitment Methods & Advertising

Describe how the study team will identify and recruit subjects. Please consider the following items and provide additional information as needed so that the IRB can follow each step of the recruitment process.

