- How will the study team identify potential participants?
- Who will first contact the potential subjects, and how?
- Will you use advertisements? If so, how will you distribute those?
- How and where will the research team meet with potential participants?
- If applicable, describe proposed outreach programs for recruiting women, minorities, or disparate populations.
- How you will minimize undue influence in recruitment?
- Attach copies of all recruiting and advertising materials (emails, verbal scripts, flyers, posts, messages, etc.).

For additional information on recruiting and advertising:

- [IRB Application Instructions - Advertisements](#)
- [PI Guide to Identification and Recruitment of Human Subjects for Research](#)

Objective 1: Kentucky Regional Extension Cooperative staff who supported the first Diabetes Learning Collaborative will recruit two stakeholders from each of the five participating clinical practices to participate in surveys and a key informant interview. KDPH will aid in recruiting three DSMES providers from the regions where the first Diabetes Learning Collaborative took place. Recruitment phone and email scripts are attached.

Objective 2: We have partnered with two healthcare organizations in Kentucky for this pilot study: Mercy Health (Mercy Health Marcum & Wallace and Mercy Health Primary Care Clinics (see LOS) and Pikeville Medical Center (see LOS). Both healthcare organizations are non-profit health centers that provide primary and preventive health care to underserved patients. Pikeville includes one participating clinic that is a federally qualified health center. Recruitment for the proposed study targets healthcare organizations in rural settings with multiple clinical sites to allow control and intervention clusters to be randomized at the clinic level within a healthcare organization. This strategy enables us to pilot our intervention in two distinct rural Kentucky settings where the population is disproportionately burdened with diabetes. We will use as control sites other clinics within the healthcare organization with similar patient populations and are of a similar size, location, and financial structure as the intervention site.

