1. Expected risks: This study presents minimum risk to participants; that is the risk is not greater than what is experienced in everyday life. The study participants are employees of healthcare clinics who will participate in intervention. There is the potential for primary participants to experience frustration due to team dynamics and/or lack of improvement in clinical diabetes care goals. The risk of frustration is described in the consent form. To minimize this risk, participant teams receive training on positive team interactions.
 2. Primary participants in the study will not be prospectively evaluated for adverse events; however, they will be encouraged to contact the study PI if they feel they have experienced an adverse event.

B. Adverse event reporting

1. Every adverse event that is reported to the principal investigator by a participant will be documented.
2. An adverse event report will be generated for each event that will include a description of the event, when and how it was reported, and a determination of attribution.
3. Recipients of the report will include the study Safety Officer (healthcare research professional not part of the study), an institutional IRB official, and the NIDDK program official.
4. Adverse events will be reported quarterly.
5. Any action resulting in a temporary or permanent suspension of this study will be immediately reported to the appropriate NIDDK program official.

III. Safety Review Plan and Monitoring

A. Sample size justification: This pragmatic cluster randomized pilot study seeks to measure the feasibility, acceptability and approximate magnitude of effectiveness of the DSMES utilization interventions; thus, four clinics will be randomized to receive the intervention and the remaining seven clinics in the two participating rural healthcare systems will serve as controls.

B. Safety and study progress reviews

1. The two principal investigators will review adverse events with the study Safety Officer quarterly given the unmasked, low risk nature of the study.
2. The two principal investigators will review study progress (e.g., recruitment, retention, protocol adherence) quarterly.
3. The annual report will include: 1) list and summary of adverse events; 2) summary of recruitment and retention and reason for dropouts; 3) whether the study is on track to be completed and accomplish the stated aims.

C. There are no Stopping Rules.**IV. Informed Consent**

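### The recruitment section makes control clinics conditional on similarity to the intervention site, while the design sections use all seven remaining clinics; the two statements need to be aligned

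*Combined protocol and SAP*

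**What the plan says.** Study Design states that "Objective 2 is a pragmatic cluster randomized trial". Two clinics per healthcare system are drawn for the intervention, four in total, and "the remaining clinics will serve as the control sites". The same section defines the primary comparison, on rates of DSMES referral, against "clinics within the healthcare system not randomized to the intervention". The Objective 2 paragraph under Records, Privacy, and Confidentiality repeats that comparison. The Data and Safety Monitoring Plan, section III.A, puts a number on it: "the remaining seven clinics in the two participating rural healthcare systems will serve as controls".

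The Objective 2 paragraph under Subject Recruitment Methods & Advertising first says that organisations with several sites were sought "to allow control and intervention clusters to be randomized at the clinic level within a healthcare organization". It ends by saying that the study will use as controls "other clinics within the healthcare organization with similar patient populations and are of a similar size, location, and financial structure as the intervention site". The same paragraph notes that "Pikeville includes one participating clinic that is a federally qualified health center".

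No section says how similarity is measured, who judges it, when it is judged, or what happens to a remaining clinic that fails it.

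**The concern.** One rule for the control arm is unconditional (all clinics not drawn). The other is conditional (clinics that resemble the intervention site). In a randomised design the intervention sites are known only once allocation has been made, so a condition that refers to them reads as a choice of controls after randomisation.

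Randomisation makes the two arms comparable in expectation only if every randomised clinic is analysed in its allocated arm. If clinics could be left out of the control arm by an undefined judgement, the primary comparison would become a matched, non-randomised one, and the stated seven controls would no longer hold. With 11 clusters, each clinic carries visible weight. The pilot is also meant to give an approximate magnitude of effect for a planned larger study.

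**Working it through.** **1. The plan's own count.** Intervention clinics: 2 per system × 2 systems = 4 (Study Design). Participating clinics: 11 (recruitment section, Objective 3; Potential Risks & Benefits). Controls: 11 − 4 = 7, which reproduces section III.A. Four plus seven uses up all 11 clinics, so the plan's arithmetic leaves room for no discarded clinic.

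**2. The statements side by side.**

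| Place | Who is a control | Number |
|---|---|---|
| Study Design | all remaining clinics; those not randomised to the intervention | 7 by subtraction |
| Records, Privacy, and Confidentiality | those not randomised to the intervention | 7 by subtraction |
| Monitoring Plan III.A | all remaining clinics | 7, stated |
| Subject Recruitment | clinics similar to the intervention site on four features | not stated; at most 7 |

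The last row matches the others only if all seven remaining clinics are similar on patients, size, location and financial structure. No section says they are.

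**3. Precision if fewer than seven were kept.** Take an unweighted comparison of clinic-level rates with equal between-clinic standard deviation σ. With k controls, SE = σ × √(1/4 + 1/k).

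- k = 7: √(0.2500 + 0.1429) = 0.627σ (reference)
- k = 6: √(0.2500 + 0.1667) = 0.645σ, ratio 1.030, or +3%
- k = 5: √(0.2500 + 0.2000) = 0.671σ, ratio 1.070, or +7%
- k = 4: √(0.2500 + 0.2500) = 0.707σ, ratio 1.128, or +13%

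The documents give no number kept, so these values of k are assumptions.

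**4. Why dropping by type after allocation matters in principle.** Suppose a system has n clinics, one of which differs from the others by D on the outcome, and the intervention has no effect. That clinic is drawn with probability 2/n and then moves the two-clinic intervention mean by D/2, an expected contribution of (2/n)(D/2) = D/n.

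- All remaining clinics kept: it is a control with probability (n − 2)/n and moves the control mean by D/(n − 2), an expected contribution of D/n. Expected difference: D/n − D/n = 0.
- Clinic left out whenever it is not drawn: the second term vanishes. Expected difference: D/n, for example D/4 with n = 4 and D/8 with n = 8. With n = 3, leaving it out would leave that system with no control.

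Neither D nor n is in the documents, and nothing says that any clinic would be left out. This shows the mechanism and does not estimate a bias.

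**The case against.** The strongest reply is that the recruitment sentence is description and not procedure. It stands in a section explaining why these organisations were approached, in a paragraph that itself says control and intervention clusters are randomised. Read that way, it says only that controls are sister clinics in the same organisation and hence broadly alike. No matching step, similarity measure or discard rule appears anywhere. Three other places use all remaining clinics, and 4 + 7 = 11 accounts for every participating clinic. This stands: the two statements can both be true, and the fault may be one of wording only.

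Three stronger readings are tempting and are not supported.

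- A reader might infer that the two rules cannot coexist. They can, if all seven clinics are similar.
- A reader might infer that the federally qualified health center would be dropped if it were not drawn. The document calls it a participating clinic, and nothing says it would be judged dissimilar. If it alone were lost, the cost in precision would be about 3%.
- A reader might compute a shift of about 0.62 between-clinic SD in the control mean by keeping the best four of seven. That requires choosing the four highest clinics on the outcome itself, whereas the sentence names patients, size, location and financial structure.

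It is also fair to say that this is a pilot with no power claim. That lowers the stakes but does not remove them, because the referral comparison is still the primary outcome. What the reply leaves unanswered is that no section confirms all seven clinics meet the condition, and that the sentence takes the intervention site as its reference.

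**Conclusion.** The discrepancy is real and its harm is conditional. Three places make every clinic not randomised to the intervention a control; one makes control status depend on similarity to the intervention site. They agree only if all seven remaining clinics are similar, which the documents do not establish. If the recruitment sentence were applied literally after allocation, randomised controls could be dropped by judgement and the primary comparison would lose the protection of randomisation. If it merely describes the pool of clinics, or if a screen was applied to all clinics before randomisation, the comparison is unharmed and only the wording is at fault.

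The size and direction of any bias cannot be derived from the documents. The loss of precision would run from about 3% in standard error (six controls kept) to 13% (four kept), assuming equal between-clinic variance and an unweighted clinic-level comparison. The point should be settled before the outcome data are analysed, since a choice of controls made after seeing results could not be repaired.

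**What to change.** Align the recruitment paragraph with Study Design, the Objective 2 data description and Monitoring Plan III.A. Suggested wording: *Every clinic included in the randomisation and not allocated to the intervention is a control clinic. All randomised clinics are analysed in the arm to which they were allocated.*

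State whether any similarity screen was used. Say that it preceded randomisation only if that is what was done. The Protocol Changes log shows the enrolment answer switched from yes to no in December 2024, so allocation has probably taken place, and the text should record actual conduct without asserting a screen that the documents do not show.

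Handle imbalance in the analysis and not by selecting controls: adjust the clinic-level comparison for the referral rate in the 9-month baseline period, which Research Procedures already has clinics report, and for healthcare system, within which clinics are randomised.

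The cost is small. No new data are needed, since control clinics already report monthly. Controls may look less closely matched in descriptive tables. The adjustment uses one or two degrees of freedom among 11 clusters: residual degrees of freedom go from 11 − 2 = 9 to 11 − 3 = 8 with one covariate, or 11 − 4 = 7 with both.

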Objective 2: Baseline measures include patient demographics (sex, race/ethnicity, insurance coverage, rural/urban distribution), A1c control (mean A1c, % of patients with A1c >9%) and blood pressure. Clinics will also report number of DSMES referrals and DSMES attendance from the 9-month baseline period. In addition to baseline data, control and intervention clinics will generate monthly reports from their electronic health record system to track DSMES referrals and A1c control. DSMES attendance will also be reported by the clinics based on feedback data from the bidirectional referral system linking clinics with DSMES providers. All data will be examined at the clinic level and will be de-identified/aggregated to the clinic level prior to being shared with our study team. The following data is being extracted from patient electronic health records by clinic staff: DSMES referrals (% referred/% eligible at the clinic level), DSMES attendance (% attended/% referred at the clinic level), A1c Data (mean A1c levels and % with A1c >9% at the following time points will be extracted from electronic health record data and de-identified/aggregated into intervention vs control clinics as well as for the subset of patients within intervention vs control clinics that attended DSMES: baseline, monthly during the intervention and for the 6 months following intervention. In addition to the data being extracted from patients' electronic health records, we will also be receiving data from the DSMES providers on patient satisfaction with the class and diabetes knowledge. This outcome will be reported to the study team monthly for all patients from study clinics who attended DSMES classes during the 9-month study + 6 month follow-up period. Patient satisfaction and diabetes knowledge will be evaluated using de-identified data from patient surveys that are routinely collected by DSMES providers for all individuals immediately following DSMES attendance. KDPH will provide the study team with de-identified data for all patients from the two participating healthcare systems who attend DSMES (aggregated to the clinic level). All data used in Objective 2 is data that is routinely collected; no additional data will be collected as a part of the study.

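### Baseline referrals are requested as a count while the primary outcome is a percentage of eligible patients; the baseline denominator, and an attendance source usable in both arms and both periods, are not clearly specified

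*Combined protocol and SAP*

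**What the plan says.** All of the measurement text is in Research Procedures, Objective 2, of the combined protocol and SAP.

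- **Baseline.** The listed baseline measures are patient demographics, A1c control and blood pressure. The text then adds: "Clinics will also report number of DSMES referrals and DSMES attendance from the 9-month baseline period".
- **Outcome.** A list introduced by "The following data is being extracted from patient electronic health records by clinic staff" defines the referral outcome as "DSMES referrals (% referred/% eligible at the clinic level" and the attendance outcome as "DSMES attendance (% attended/% referred at the clinic level". A1c follows as a mean and a percentage above 9%, with time points that include baseline. The bracket opened at the A1c item is never closed.
- **Attendance source.** "DSMES attendance will also be reported by the clinics based on feedback data from the bidirectional referral system linking clinics with DSMES providers". Attendance is also in the health-record list just described, and the paragraph adds: "KDPH will provide the study team with de-identified data for all patients from the two participating healthcare systems who attend DSMES (aggregated to the clinic". That sentence gives no period.
- **What the referral system is.** Study Design, Objective 2, lists as intervention components "an automated patient identification system and bidirectional e-referral system connecting clinics to the DSMES providers". No installation date is given.
- **Analysis.** Study Design names referrals as the primary outcome and compares their rates between intervention and control clinics. No baseline-adjusted model is stated. The sample size justification in the Data and Safety Monitoring Plan gives four intervention and seven control clinics.
- **Full data list.** Data Collection & Research Materials refers to an attached data collection summary that is not reproduced in the documents.

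**The concern.** A clinic's number of referrals depends on its size as well as on its referral practice, and it may count one patient more than once. A percentage of eligible patients does neither. If only the count is kept for the baseline, the primary outcome has no baseline value in its own units. Change from baseline, or adjustment for the baseline rate, could then not be carried out from the data sent to the study team, which arrive already aggregated by clinic.

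Attendance has a related problem. A figure that depends on feedback from an intervention component may be missing before rollout and may be collected differently in control clinics. A difference between arms could then partly be a difference in measurement.

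With 11 clinics, chance imbalance in prior referral practice is a real possibility. The pilot is meant to indicate the approximate size of the effect and to supply preliminary data for a larger study, so both points bear on its main product.

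**Working it through.** The plan gives no power or precision figure to reproduce. The check has three steps.

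**1. Baseline and outcome definitions side by side**

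| Measure | Baseline | Outcome | Same metric? |
|---|---|---|---|
| Referrals (primary) | number over 9 months | percentage of eligible patients | not as written |
| Attendance | number over 9 months, if the word number covers both items | attended over referred | can be formed from the two counts |
| A1c | mean and % above 9% | mean and % above 9% | yes |

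I read the referral outcome as referred patients divided by eligible patients. The time points that include baseline come after the bracket opened at A1c, so they read most naturally as applying to A1c only.

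**2. Can the outcome be formed from the baseline counts?** The counts below are assumed, since the documents give none.

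- Referrals: 30 referrals with 100, 200 or 400 eligible patients give 30/100 = 30%, 30/200 = 15% or 30/400 = 7.5%. Without the denominator the rate is undetermined.
- Attendance: 12 or 6 attended of 30 referred give 12/30 = 40% or 6/30 = 20%. Here the two counts are enough, provided that attended patients can be counted at baseline.

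**3. What the count costs as a covariate.** None of these inputs is in the documents: mean clinic rate 10%, SD 5 percentage points, mean of 455 patients per clinic, lognormal clinic size, beta-distributed rates, binomial sampling, and baseline and follow-up rates linked through a normal copula. The correlation of the underlying rates and the coefficient of variation (CV) of clinic size were varied.

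Adjusting for a covariate with squared correlation r² to the follow-up rate leaves a fraction 1 − r² of the between-clinic variance. The ratio of interval widths, count against rate, is therefore sqrt[(1 − r²_count)/(1 − r²_rate)].

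- Correlation 0.7, CV 0.5: r²_rate = 0.397 and r²_count = 0.187, so sqrt(0.813/0.603) = 1.16, or 16% wider.
- Correlation 0.7, CV 0.3: r²_rate = 0.406 and r²_count = 0.288, so sqrt(0.712/0.594) = 1.095, or just under 10% wider.

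Widening of the interval with the count instead of the rate (simulated, good to about one percentage point):

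| Correlation | CV 0.1 | CV 0.2 | CV 0.3 | CV 0.5 | CV 0.8 |
|---|---|---|---|---|---|
| 0.3 | <1% | <1% | 1% | 2% | 3% |
| 0.5 | <1% | 2% | 4% | 6% | 8% |
| 0.7 | 2% | 5% | 9-10% | 16% | 20% |
| 0.9 | 5% | 16% | 27% | 43% | 51% |

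These are large-sample ratios. They leave out the degree of freedom that a covariate uses, which is the same for the count and the rate.

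**The case against.** The strongest reply is that this is an ambiguity and not a demonstrated gap. The unclosed bracket allows a reading in which baseline applies to the whole extraction list, so that the referral percentage is collected at baseline after all. The list of baseline measures is not worded as exhaustive, and the complete data list is in an attachment that is not shown. All of this stands, and it is why the point is that the text is unclear and not that the denominator is absent. If the wider reading is right, the paragraph asks for two different baseline referral measures, and the text still needs to be reconciled.

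Several stronger readings are tempting, and the documents do not support them:

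- **That no baseline measure matches its outcome.** A1c matches, and attended over referred can be formed if both baseline items are counts.
- **That the referral system is the only attendance source, or is known to be absent at baseline.** Health-record extraction and KDPH attendee data are also named. Absence before rollout is an inference from the system's place in the intervention.
- **That a baseline rate is lost for good.** The study team cannot rebuild it from the aggregates, but clinic staff can rerun the query.
- **That referrals are the only check on imbalance.** Demographics, A1c and blood pressure are also collected.
- **That the primary analysis fails.** A randomised comparison of rates does not need a baseline value, and none is planned.

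The precision argument is also fairly criticised. A widening of 16% holds at one assumed pair of inputs, a correlation of 0.7 and a size CV of 0.5. Subject Recruitment Methods & Advertising describes control clinics as similar in size to intervention clinics, which points to the lower CV columns.

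**Conclusion.** The point holds as a matter of specification, for the primary outcome and for attendance. Baseline referrals are described as a count, the outcome as a percentage of eligible patients, and a baseline denominator is not clearly provided for. The attendance source stated for clinic reporting is an intervention component, and no source is designated for both arms and both periods.

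The between-arm comparison is not invalid. The loss is the option of a like-for-like adjustment with 4 against 7 clinics. Its size rests on assumptions outside the documents: under 1% to about 50% in interval width over correlations of 0.3 to 0.9 and size CVs of 0.1 to 0.8, and about 5-10% at correlation 0.7 and CV 0.2 to 0.3. At low correlation the gain is negligible. That a count alone does not determine a rate depends on none of these assumptions. The unseen data collection summary could settle the denominator question, and if it does, the main text should say so. This is a change worth making, not an essential one.

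**What to change.** In Research Procedures, Objective 2:

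1. Have each of the 11 clinics report, for the 9-month baseline, the number of unique eligible patients and the number of unique patients with at least one referral. Use the same health-record query and the same eligibility definition as at follow-up, applied as of the baseline dates.
2. State that the resulting baseline rate is the adjustment covariate for the referral outcome.
3. Close the bracket in the extraction list, so that it is clear which measures the baseline time point covers, and align the attached data collection summary.
4. Name one attendance source available in both arms and both periods. The clinic-level KDPH attendee data already planned are a natural choice if the request is extended to the baseline. KDPH supplies the attended count, so the referred count still comes from the clinic query.
5. Record the limit of that source. Background reports 90 recognised programs in Kentucky, of which KDPH's is the largest. Attendance elsewhere would be missed equally in the two arms only if referral patterns are similar.

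The cost is one retrospective query per clinic, one extended aggregate request to KDPH and a few lines of text. No new patient contact or identifiable data are needed.
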